8 STUDY VISITS AND PROCEDURES

8.1 Study timeline

8.2 Schedule of assessments

Time point relative to randomisation		
Screening		A
Screening		B
Randomisation (0 week)	Intervention	Control
Pre-intervention assessment (1 week)	C	C
Training in intervention (1 week)	D	E
Completion of intervention (1 week to 5 weeks)	F H	G H
Post-intervention assessment (5 weeks)	C	C
Post-intervention assessment (3 months)	C	C
Post-intervention assessment (6 months)	C	C
TALI offered to control group (6 months)		I
Intervention (6 months to 7 months)		F
A	Questionnaire screening for attentional deficits, and other inclusion/exclusion is emailed to families for completion.	
B	Screening for IQ criteria completed for children who have not undergone IQ testing post injury, or within the past two years.	
C	A face to face assessment session (2 - 2.5 hours) is held at MCRI. A researcher will administer the SSS, TEA-Ch2 selective attention and sustained attention subtests, the child ANT, the Anticipated Response Task, the Corsi Block-Tapping Test, a digit span task, the PEERS, the WIAT-II, and the IMS (pre-intervention only). Parents will be asked to complete the SWAN, the CSHQ, the PECL, the GHQ-12, the CDS-P, the SCAS-P, and the PEERS-Q.	
D	Parents and children will be trained in the use of the TALI program. Researchers will provide a tablet with the intervention program and parent guidebook.	
E	Parents and children will be trained in the use of the control task program. Researchers will provide a tablet with the control program and parent guidebook.	
F	Children will complete TALI modules for 20 mins per day, 5 days per week for 5 weeks, under the supervision of a parent.	
G	Children will complete control task modules for 20 mins per day, 5 days per week for 5 weeks, under the supervision of a parent.	
H	Families will receive weekly phone contact from a researcher to offer support throughout the intervention, address any technical issues that arise, and to monitor compliance.	
I	Families in the control group will be offered access to the TALI program.	

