5.2.2 Exclusion criteria

Participants meeting any of the following criteria will be excluded from the study:

- Is unable to comprehend or follow study instructions, including where sensory or physical impairments are present
- Has had a previous brain injury
- Has a diagnosed or borderline intellectual delay as defined as IQ<80 on the WASI/WPPSI
- Has a prior diagnosis of developmental delay.
- More than 6 years has passed since the time of injury, or in the case of ABI due to cancers, since the conclusion of treatment (including chemotherapy).

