8.3 Screening

Stage 1 Screening

The first stage of screening will be undertaken by researchers based on information gained from the VPRS database and audit of medical records and will be based on the inclusion criteria outlined in section 5.2.1. The parents of children who meet the inclusion criteria will be contacted via the means outlined in section 5.3. Once informed consent for participation is received by the researchers, families will be invited to participate in the second stage of screening.

Stage 2 Screening

The second stage of screening will be conducted online. Parents/guardians of participants will be sent an email inviting them to participate in the screening process. Parents will be asked to complete a demographic and medical questionnaire, and the Conners 3 or Conners EC depending on the age of the child. Both the Conners 3 and Conners EC will be administered and scored via the online Conners platform. The Conners is used to measure ADHD symptoms and in this study, will be used to determine whether children meet the criteria of an attentional deficit needed to participate in the study. An attentional deficit will be defined as a t score >60 on either of the two inattention subscales of the Conners 3, or on the inattention/hyperactivity subscale of the Conners EC.

If the screening assessments have not been completed after a period of two weeks, a member of the research team will contact participants to follow up. This will entail one documented reminder email, and one follow up Short Message Service (SMS) or phone call. If a period greater than 2 weeks has passed from the first reminder contact date then participants will be recorded as having 'incomplete' screening and they will not be contacted further.

Stage 3 Screening

Following completion of the second stage of screening, researchers will assess eligibility for the study based on the exclusion criteria listed in section 5.2.2.

In cases where children meet all other eligibility criteria, children who have not undergone IQ testing post injury and within the last two years, will be asked to complete either the WASI or the WPPSI (dependent on age). The WASI/WPPSI will be administered by a trained member of the research team at MCRI. Should the child be unable to attend MCRI, an offer will be made to conduct this assessment at the child's school or within the family home.

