8.4 Baseline

Enrollment/Baseline Visit (Visit 1, Week 1)

Pre-intervention assessments will be conducted by [name], [name], [name] or an MCRI research assistant. These assessments will take place at MCRI. Participants may find the assessment sessions to be tiring and small breaks should be provided when needed. The assessments will comprise the following tasks and are estimated to take 2 – 2.5 hours to complete:

1. Stanford Sleepiness Scale – The SSS is a single item self-report assessment of current levels of sleepiness. Children are asked to rate their current level of sleepiness on a 7 point scale ranging from 1 (very awake) to 7 (very sleepy). This measure is expected to take no more than 5 minutes to complete.
2. Test of Everyday Attention for Children (Tea-Ch2) will be used to assess attention. Children aged 4 to 7 will complete 4 subscales from junior version which are either facilitated by or wholly completed on the computer. The subtests are designed to assess selective attention (Balloon Hunt; Balloons 5) and sustained attention (Simple Reaction Time; Sustained Attention to Response Task). Children aged 8 to 9 years will complete 4 equivalent subscales from the older version (Hector Cancellation; Hector-B; Simple RT and SART). The battery should take no more than 20 minutes to complete. This measure provides both raw score and scaled scores for each of the subtests.
3. Child Attention Network Task (ANT) – a child friendly version of the flanker task which is suitable for children aged 4 years and above. The Anticipated Response task - a stop signal task that measures the ability to rapidly prevent already initiated actions. The Child ANT would enable assessment of interference control and the Anticipated Response task assessment of response inhibition, both aspects of attentional control. These measures are administered on a laptop and should take no more than 30 minutes in total to complete.
4. Corsi Block-Tapping Test (forwards and backwards) – Visuospatial working memory. Children are required to replicate a sequence by clicking the corresponding blocks on the screen. This test is administered on a laptop and should take no more than 10 minutes to complete. This measure provides a raw score of the number of sequences children have correctly replicated.

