3. The Parent’s Experience of Child Illness (PECI) – The Peci is a parent-report measure of family environment designed to measure parental adjustment relating to their child’s chronic illness. The Peci comprises four subscales; Guilt and Worry, Unresolved Sorrow and Anger, Long-term Uncertainty, and Emotional Resources. The Peci is widely used in paediatric ABI samples. The measure comprises 25 items, each rated on a 5-point Likert Scale.
4. The General Health Questionnaire (GHQ-12) - The GHQ-12 is a commonly used 12-item self-report instrument designed to measure mental health in adults within community settings.
5. Children’s Depression Scale 3rd Ed.(CDS-P) – This measure is a 50 item, parent report measure of child depression symptoms. This measure has good reliability and validity for assessing depressive symptoms and wellbeing in children.
6. Spence Children’s Anxiety Scale –Parent (SCAS-P) – This measure is a 38 item parent report questionnaire, designed to measure anxiety symptoms relating to DSM anxiety disorders including panic disorder, generalised anxiety disorder, social phobia, and separation anxiety disorder, as well as school phobia. The SCAS is appropriate for use with children with an Acquired Brain Injury.
7. Paediatric Evaluation of Emotions, Relationships and Sociability Questionnaire (PEERS-Q) – This measure is a 55 item parent report questionnaire, designed to measure social skills in daily life. The PEERS-Q is appropriate for use with children with an Acquired Brain Injury.

Following the completion of the pre-intervention assessment, children and their parent or guardian will be given their allocated intervention tablet and handbook.

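### Randomisation is scheduled before the baseline visit although no trial procedure needs the allocation until that visit ends, so a child can be randomised and have no baseline score

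*Protocol*

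**What the plan says.** The schedule in Protocol section 8.2 is headed "Time point relative to randomisation". It lists two screening steps, then "Randomisation (0 week"), then "Pre-intervention assessment (1 week"), with training in the program also at week 1. Section 8.4 agrees on the timing: "Enrollment/Baseline Visit (Visit 1, Week 1").

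Section 8.3 describes what happens before randomisation:
- Stage 1 works from the rehabilitation service database and medical records.
- For stage 2, "The second stage of screening will be conducted online"; parents complete it.
- Stage 3 checks the exclusion criteria of section 5.2.2. One of these is "Is unable to comprehend or follow study instructions, including where sensory or physical impairments are present". No test or trial of the tasks is named for it.
- Direct contact with the child is required only where IQ has to be tested: "children who have not undergone IQ testing post injury and within the last two years, will be asked to complete either the WASI or the" alternative Wechsler scale, according to age.

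On the use of the allocation, section 8.4 states: "Following the completion of the pre-intervention assessment, children and their parent or guardian will be given their allocated intervention tablet and handbook".

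Section 13.2.1 defines the intention-to-treat population in terms of enrolled children. Section 7 sets 1:1 blocks of 4 within three severity strata.

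**The concern.** Randomisation is best placed as late as practicable, just before the arms begin to differ. Here it comes before the first session in which the child meets the study's computerised tasks. That session lasts 2 to 2.5 hours, and section 8.4 itself warns that it may be tiring. The children are as young as 4 and have a brain injury and an attention deficit, so some failures to attend or to complete the battery are foreseeable.

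A child lost at that point has been randomised and has used a place in a block, but has no baseline score. The analysis in section 13.2.3 compares each participant with his or her own baseline. The protocol also does not settle whether the child is in the analysis population: randomised at week 0, but perhaps never enrolled if enrolment happens at Visit 1. At stake are complete data, a clear intention-to-treat set and some power.

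**Working it through.** **Order of events**

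| Step | Timing | Source | Does it use the allocation? |
|---|---|---|---|
| Records and online screening | before week 0 | 8.3, stages 1-2 | no |
| Exclusion check; IQ test if needed | before week 0 | 8.3, stage 3 | no |
| Randomisation | week 0 | 8.2 | creates it |
| Baseline battery, called the enrolment visit | week 1 | 8.2, 8.4 | no; assessors unaware of arm (7.1) |
| Tablet handed over, training | week 1, after the battery | 8.2, 8.4 | first use with the family |

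Two things follow. No trial procedure between randomisation and the end of the battery depends on the arm. And a child who already has a qualifying IQ result can reach randomisation with no required in-person contact. How many children this covers cannot be worked out, because no share is given. The IQ rule also differs between sections: 8.2 joins its two conditions (no post-injury test, none in the past two years) with *or*, 8.3 with *and*. The two need to be reconciled, since they decide who is seen beforehand.

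**Reproducing the protocol's sample size (section 13.1)**

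Inputs: repeated-measures ANOVA, between factors; 2 groups; m = 2 measurements; correlation ρ = .5; alpha .05; power .8; f = .4 or .25.

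Noncentrality λ = N·f²·m / [1 + (m − 1)ρ], with 1 and N − 2 degrees of freedom.

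- f = .40, N = 40: λ = 40 × 0.16 × 2 / 1.5 = 8.53; power 81.2%.
- f = .25, N = 98: λ = 98 × 0.0625 × 2 / 1.5 = 8.17; power 80.8%.

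These are the smallest even totals that reach 80%, and they match the stated 40 and 98.

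**Scale of a loss between randomisation and baseline**

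The protocol gives no rate, so 5-10% is an assumption: 0.05 × 80 = 4 and 0.10 × 80 = 8. Taking these children as contributing no data and not being replaced:

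| Children with data | λ at f = .25 | Power, f = .25 | Power, f = .40 |
|---|---|---|---|
| 80 | 6.67 | 72.2% | 98.3% |
| 76 (5% lost) | 6.33 | 70.0% | 97.8% |
| 72 (10% lost) | 6.00 | 67.6% | 97.2% |

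To keep 80 with a baseline score under the present order, 80 / 0.95 = 84.2, so 85, or 80 / 0.90 = 88.9, so 89, would have to be randomised. The gap between 72.2% and 80% at f = .25 comes from planning 80 rather than 98 and has nothing to do with this point.

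**The case against.** Several counter-arguments have force.

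- **The exclusion check precedes randomisation.** Stage 3 covers the criterion on following instructions, informed by records, the parent's questionnaire and any IQ session. A reader might infer that inability is discovered only after randomisation, or that children are often unseen until then. Neither is supported: the check exists, and the share with a qualifying IQ test is not given. What stands is that no pre-randomisation step tries the study tasks, so some cases can still surface at Visit 1.
- **There is no shown route to bias.** A reader might infer that the randomised comparison is compromised because baseline is measured once an allocation exists. Section 7.1 keeps assessors unaware of the arm, and nothing says that families learn it before the tablet arrives. Loss in this interval is therefore unlikely to depend on the arm. Gaps in blocks of 4 have little effect on balance, and unfinished blocks can occur in three strata anyway. This objection stands.
- **The interval may be shorter than a week.** The five-week program is shown as running from week 1 to week 5, which suggests that week 1 means the first week. That shortens the gap but does not change the order.
- **Lost children may be replaced.** Section 8.9.3 continues recruitment towards the required sample size, which could restore numbers. It does not give the lost child a baseline score or settle that child's place in the analysis set.
- **Early randomisation has a practical use.** Section 15 has each tablet carry only the allocated program, so knowing the arm beforehand lets a single tablet be prepared. This is a real convenience, and it is the price of the fix.

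**Conclusion.** The point holds as a sequencing weakness that is cheap to remove. The order is stated in both section 8.2 and section 8.4, and it allows a child to be randomised with no baseline score and an unclear place in the intention-to-treat set. The harm is mainly missing data and lost precision. Under the assumed 5-10% loss without replacement, it is 2.2 to 4.6 percentage points of power at f = .25 (72.2 − 70.0 and 72.2 − 67.6) and about 1 point at most at f = .40 (98.3 − 97.2).

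These figures use the ANOVA of section 13.1 as a yardstick; the planned growth-curve analysis would give somewhat different values. The documents support neither a claim of bias nor any statement about how frequently children reach randomisation unseen.

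**What to change.** Amend sections 8.2 and 8.4 so that the baseline battery and a final check of the existing exclusion criteria come first. The independent researcher of section 7.1 then randomises the child at the end of Visit 1 and issues the allocated tablet. Define week 0 as that visit. The age criterion in section 5.2.1, already tied to randomisation, would then be applied there, and the later visit weeks should be restated from the new origin. With enrolment and randomisation at the same visit, the wording of section 13.2.1 becomes unambiguous.

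The cost is a protocol amendment, plus having the independent researcher reachable at every baseline visit with a tablet for either arm ready. No visit, assessment or staff role is added. Families who do not attend Visit 1 are still lost to recruitment, and later drop-out is unaffected; the change only keeps pre-baseline losses out of the randomised set.

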8.3 Screening

Stage 1 Screening

The first stage of screening will be undertaken by researchers based on information gained from the VPRS database and audit of medical records and will be based on the inclusion criteria outlined in section 5.2.1. The parents of children who meet the inclusion criteria will be contacted via the means outlined in section 5.3. Once informed consent for participation is received by the researchers, families will be invited to participate in the second stage of screening.

Stage 2 Screening

The second stage of screening will be conducted online. Parents/guardians of participants will be sent an email inviting them to participate in the screening process. Parents will be asked to complete a demographic and medical questionnaire, and the Conners 3 or Conners EC depending on the age of the child. Both the Conners 3 and Conners EC will be administered and scored via the online Conners platform. The Conners is used to measure ADHD symptoms and in this study, will be used to determine whether children meet the criteria of an attentional deficit needed to participate in the study. An attentional deficit will be defined as a t score >60 on either of the two inattention subscales of the Conners 3, or on the inattention/hyperactivity subscale of the Conners EC.

If the screening assessments have not been completed after a period of two weeks, a member of the research team will contact participants to follow up. This will entail one documented reminder email, and one follow up Short Message Service (SMS) or phone call. If a period greater than 2 weeks has passed from the first reminder contact date then participants will be recorded as having 'incomplete' screening and they will not be contacted further.

Stage 3 Screening

Following completion of the second stage of screening, researchers will assess eligibility for the study based on the exclusion criteria listed in section 5.2.2.

In cases where children meet all other eligibility criteria, children who have not undergone IQ testing post injury and within the last two years, will be asked to complete either the WASI or the WPPSI (dependent on age). The WASI/WPPSI will be administered by a trained member of the research team at MCRI. Should the child be unable to attend MCRI, an offer will be made to conduct this assessment at the child's school or within the family home.

8.4 Baseline

Enrollment/Baseline Visit (Visit 1, Week 1)

Pre-intervention assessments will be conducted by [name], [name], [name] or an MCRI research assistant. These assessments will take place at MCRI. Participants may find the assessment sessions to be tiring and small breaks should be provided when needed. The assessments will comprise the following tasks and are estimated to take 2 – 2.5 hours to complete:

1. Stanford Sleepiness Scale – The SSS is a single item self-report assessment of current levels of sleepiness. Children are asked to rate their current level of sleepiness on a 7 point scale ranging from 1 (very awake) to 7 (very sleepy). This measure is expected to take no more than 5 minutes to complete.
2. Test of Everyday Attention for Children (Tea-Ch2) will be used to assess attention. Children aged 4 to 7 will complete 4 subscales from junior version which are either facilitated by or wholly completed on the computer. The subtests are designed to assess selective attention (Balloon Hunt; Balloons 5) and sustained attention (Simple Reaction Time; Sustained Attention to Response Task). Children aged 8 to 9 years will complete 4 equivalent subscales from the older version (Hector Cancellation; Hector-B; Simple RT and SART). The battery should take no more than 20 minutes to complete. This measure provides both raw score and scaled scores for each of the subtests.
3. Child Attention Network Task (ANT) – a child friendly version of the flanker task which is suitable for children aged 4 years and above. The Anticipated Response task - a stop signal task that measures the ability to rapidly prevent already initiated actions. The Child ANT would enable assessment of interference control and the Anticipated Response task assessment of response inhibition, both aspects of attentional control. These measures are administered on a laptop and should take no more than 30 minutes in total to complete.
4. Corsi Block-Tapping Test (forwards and backwards) – Visuospatial working memory. Children are required to replicate a sequence by clicking the corresponding blocks on the screen. This test is administered on a laptop and should take no more than 10 minutes to complete. This measure provides a raw score of the number of sequences children have correctly replicated.
5. Digit Span task (forwards and backwards) – Auditory working memory. Children are required to replicate a sequence of digits by selecting them from a circle of digits on the screen. This task is administered on a laptop and should take no more than 5 minutes to complete. This measure provides a raw score of the number of accurately recalled digits.
6. Paediatric Evaluation of Emotions, Relationships and Sociability (PEERS) – Measures social skills. This is a game-based computerised task which is administered via a touchscreen tablet. Children will be asked to complete the Emotion Perception and Emotion Recognition subtests from the Social Cognition Domain, and the Non-verbal Gestures and Social Perception subtests from the Social Communication Domain. These domains were selected as there are the areas of social functioning thought to be most impacted in children with Acquired Brain Injuries. This task should take no more than 10 minutes to complete.
7. The Wechsler Individual Achievement Test II (WIAT II) is a standardised measure of mathematics ability. The WIAT II can be used with both children and adults. Children will complete the numerical operations and mathematical reasoning subtests to give a measure of mathematics ability. Starting points are based on the child's age and children progress until they make six consecutive errors. Completion time is expected to take no more than 30 minutes.
8. Intrinsic Motivation Scale – This is a child-specific 18 item self-report measure of motivation with regards to school and schoolwork. This measure provides a score relating to the child's overall motivation. This task should take no more than 10 minutes to complete.

Parents will be asked to complete the following, note the time to complete all measures is estimated at less than 2 hours:

1. Strengths and Weaknesses of ADHD symptoms and normal behaviour – The SWAN is an 18 item parent report questionnaire based on DSM-5 criteria for ADHD. The SWAN provides raw scores on children inattentive, and impulsive/hyperactive behaviours. Higher scores on this measure indicate greater attention difficulties.
2. Children’s Sleep Habits Questionnaire – The CSHQ is a 33 item parent report sleep screening assessment tool. The CSHQ provides a total score and 8 subscale scores, assessing key domains of sleep, both medical and behavioural. Higher scores across subscales indicate greater sleep concerns.
3. The Parent’s Experience of Child Illness (PECI) – The Peci is a parent-report measure of family environment designed to measure parental adjustment relating to their child’s chronic illness. The Peci comprises four subscales; Guilt and Worry, Unresolved Sorrow and Anger, Long-term Uncertainty, and Emotional Resources. The Peci is widely used in paediatric ABI samples. The measure comprises 25 items, each rated on a 5-point Likert Scale.
4. The General Health Questionnaire (GHQ-12) - The GHQ-12 is a commonly used 12-item self-report instrument designed to measure mental health in adults within community settings.
5. Children’s Depression Scale 3rd Ed.(CDS-P) – This measure is a 50 item, parent report measure of child depression symptoms. This measure has good reliability and validity for assessing depressive symptoms and wellbeing in children.
6. Spence Children’s Anxiety Scale –Parent (SCAS-P) – This measure is a 38 item parent report questionnaire, designed to measure anxiety symptoms relating to DSM anxiety disorders including panic disorder, generalised anxiety disorder, social phobia, and separation anxiety disorder, as well as school phobia. The SCAS is appropriate for use with children with an Acquired Brain Injury.
7. Paediatric Evaluation of Emotions, Relationships and Sociability Questionnaire (PEERS-Q) – This measure is a 55 item parent report questionnaire, designed to measure social skills in daily life. The PEERS-Q is appropriate for use with children with an Acquired Brain Injury.

Following the completion of the pre-intervention assessment, children and their parent or guardian will be given their allocated intervention tablet and handbook.

